## Funder

The NIHR HTA has provided Project Grant funding for this study.

This protocol describes the above study and provides information about the procedures for entering participants. Every reasonable care has been taken in the drafting of this protocol. However, corrections or amendments may be necessary; any changes will be circulated to investigators in the study. Problems relating to this study should be referred, in the first instance, to the Chief Investigator.

This study will adhere to the principles outlined in the NHS Research Governance Framework for Health and Social Care (2nd edition). It will be conducted in compliance with the protocol, the Data Protection Act and other regulatory requirements as appropriate, including Good Clinical Practice (GCP).

## **1. STUDY SUMMARY**

- TITLE IGRA in Diagnostic Evaluation of Active TB ('IDEA')
- **DESIGN** Prospective cohort study, analysing testing regimes for 1,012 *suspected active TB* volunteers.
  - **AIMS** The overall aim of this study is to compare the diagnostic accuracy of the *ELISpot* based (T-SPOT.TB) and *ELISA* (QunatiFERON-TB GOLD in-tube) based IGRAs, with conventional diagnosis of *suspected active TB*, in routine NHS clinical practice.
- **POPULATION** Adults presenting with *suspected active TB* aged 16 years-of-age, or over.
  - **ELIGIBILITY** Adults (male and female) presenting with *suspected active TB* (aged 16 years-of-age, or over) without a history of TB medication.
  - **DURATION** 3 Years.

## 2. GLOSSARY OF ABBREVIATIONS

AE	Adverse Event
ATB	Active TuBerculosis
BAL	BronchoAlveolar Lavage
BCG	Bacille Calmette-Guérin
CD4	Cluster of Differentiation IV
CI	Confidence Interval
DNA	Deoxyribonucleic acid
DMC	Data Monitoring Committee
ELISA	Enzyme-Linked Immunoabsorbent Assay
GCP	Good Clinical Practice
HIV	Human Immunodeficiency Virus
HTA	Health Technology Assessment
IGRA	Interferon-Gamma Release Assay
LTBI	Latent TuBerculosis Infection
NHLI	National Heart and Lung Institute
NHS	National Health Service
NICE	National Institute for Health and Clinical Excellence
NIHR	National Institute of Health Research
M. tuberculosis	Mycobacterium tuberculosis
PBMCs	Peripheral Blood Mononuclear Cells
ROC	Receiver Operating Characteristic
SAE	Serious Adverse Event
SSA	Site Specific Assessment
ТВ	TuBerculosis
TSC	Trial Steering Committee
TST	Tuberculin Sensitivity Test
UK	United Kingdom
WHO	World Health Organisation

## **KEYWORDS**

Active TB (ATB), Assay, BCG, Diagnostic Test, ELISA, ELISpot, IGRA, TuBerculosis (TB), TST.

## 3. INTRODUCTION

#### 3.1 Research Aims

The aim of this study is to compare the accuracy of diagnostic strategies, including a comparison between existing interferon-gamma release assays (IGRAs) and conventional diagnostic testing. The role of IGRAs for patients (termed *'participants'* from here on) who have been diagnosed as having suspected active tuberculosis (ATB) will also be defined.

The study will determine sensitivity, specificity, positive and negative predictive values and likelihood ratios of the ELISpot-based IGRA and the ELISA-based IGRA for diagnosis of active tuberculosis, in routine clinical practice. The study will be measured against a validated pre-defined composite reference standard for active tuberculosis. Next-generation IGRAs will be evaluated in parallel. The accuracy of these different testing strategies will be compared and an optimal testing algorithm defining the precise role of these technologies in the diagnostic work-up of suspected active tuberculosis in the NHS (National Health Service) will be developed. Health economic analysis, from an NHS perspective, will determine the cost-effectiveness of each testing strategy, following NICE (National Institute for Health & Clinical Excellence) guidelines.

#### 3.2 Background to research

Globally, in 2007, an estimated 9.27 million incident cases of Tuberculosis (TB) indicated a strong and continued increasing trend in the burden of this infectious disease. Over 8,000 cases of TB were reported in the UK in 2007 (incidence rate of 13.8 per 100,000 population) with the main burden of disease concentrated in specific urban areas; 39% of all cases were in London with the incidence in Leicester City at 67 per 100,000 population. The majority of cases occurred in two distinct categories: in young adults and among those born outside of the United Kingdom (UK). Diagnosis of active TB disease is central to controlling the TB epidemic. However, the poor speed and sensitivity of existing diagnostic tools delays diagnosis and treatment of active TB.

The risk of developing TB infection can be dramatically increased when a person is HIV (human immunodeficiency virus) infected. Infection with TB and HIV is commonly termed 'TB and HIV co-infection'. The severe nature of HIV in the presence of TB has led some to consider it "the cursed duet", mainly because of a combined duel effect upon the disease process, which can cause rapid and progressive health deterioration. It has been estimated that in 2003, 8.3% of TB cases in England and Wales were co-infected with HIV and in 2007, an estimated 1.37 million (15%) of incident TB cases globally were HIV-positive.

TB is caused by an active infection with *Mycobacterium tuberculosis* (*M. tuberculosis*). Reliable determination of infection status, whether active or latent, could accelerate diagnostic assessment by enabling rapid exclusion of TB. Current conventional methods of diagnosing active TB primarily rely upon the identification of bacilli through microscopy, nucleic acid amplification and culture which may take several weeks to confirm a diagnosis. While highly specific for *M. tuberculosis* these techniques have poor sensitivity. Clinical symptoms and radiological features indicative of TB, histology (where appropriate) and on occasion the use of the tuberculin skin test (TST) can also be used to determine infection status. However, the sensitivity of TST, which measures the delayed-type hypersensitivity response to intradermal inoculation of a crude mixture of *M. tuberculosis* antigens, is insufficient for reliable exclusion of TB from the differential diagnosis. Poor sensitivity, especially in HIV-infected

patients, often confounded by prior BCG (Bacille Calmette-Guérin) vaccination, can produce false-positive results.

There is an urgent need to develop alternative diagnostic modalities, able to rapidly and reliably exclude the diagnosis of TB; improved diagnosis is essential to contain and reverse the rising global burden of this disease. New blood tests, called interferon gamma release assays (IGRAs) have recently been developed to diagnose *M. tuberculosis* infection. IGRAs detect interferon gamma release from T cells (lymphocytes that play a key role in cell-mediated immunity) in response to *M. tuberculosis*-specific antigens, which are absent from the BCG vaccine and most environmental mycobacteria. Test results are not confounded by previous BCG vaccination, conferring higher specificity than TST. An important component to effective and efficient clinical diagnosis, results are available within 24 hours and do not require the patient to make a return visit. IGRA has been recommended by UK, European and North American guidelines to diagnose latent tuberculosis infection (LTBI) although its role in active TB remains unclear.

The sensitivity and specificity of IGRAs compared to TST in active TB have been compared in a large number of studies. IGRAs are more specific than the TST for diagnosing *M. tuberculosis* infection and ELISpot is more sensitive than TST for diagnosing TB. Unfortunately, IGRAs, in common with TST, are unable to distinguish active from latent infection and the causal relationship produced is (currently) one of poor specificity for active TB. However, with an appropriately high sensitivity in active TB disease, IGRAs could potentially allow the rapid exclusion of active TB disease within 24 hours; notably, weeks before culture results would (typically) become available. The two types of commercially available IGRAs are the whole-blood enzyme-linked immunosorbent assay (ELISA) and enzyme-linked immunospot assay (ELISpot) both utilising peripheral blood mononuclear cells (PBMCs). The whole-blood ELISA is available commercially as QuantiFERON-TB Gold In-tube (QFT-GIT, Cellestis, Carnegie, Australia) and the ELISpot is available commercially as T-SPOT.*TB* (Oxford Immunotec, Abingdon, United Kingdom).

Diagnostic accuracy of existing ELISpot-based IGRA and ELISA-based IGRA, have not been compared directly 'head-to-head' in suspected active TB in the UK, nor comprehensively assessed in immunosuppressed patients. There is uncertainty in the role and clinical utility of IGRAs in the diagnostic work up of suspected TB and the cost-effectiveness in this particular setting.

#### Key issues specific to this research study include:

A) The first study to compare the diagnostic accuracy of both types of IGRA with conventional diagnostic testing for active TB in the UK;

B) The largest cohort globally to-date for evaluation of IGRAs; and

**C)** The largest study evaluating IGRA in HIV-TB co-infection, globally. The results of this study will influence tuberculosis control and elimination policy here in the UK, in Europe and North America.

#### 3.3 NIHR HTA report detailing outputs of the research

A comprehensive report for the NIHR HTA will be produced. This will include recommendations based upon the evidence generated in this study, on the accuracy and clinical utility of diagnostic strategies that include IGRAs, and how they compare to conventional diagnostic testing for the work-up of patients suspected of active TB. An evidence-based optimal testing algorithm that defines the role of IGRAs in the diagnostic work-up of suspected active TB in the NHS will be presented and the cost-effectiveness (from an NHS perspective) of each testing strategy will be quantified and compared. Recommendations will also be provided for TB patients co-infected with HIV.

The report will summarize findings particularly relevant to UK TB control policy, including health and health economic effects on TB transmission in the UK. It is intended that the research will also be

disseminated through peer-reviewed publications, conference presentations and engagement with policy makers (Department of Health and Health Protection Agency), patients and the public via local clinical networks in London and voluntary sector agencies such as *TB Alert*.

## 4. STUDY OBJECTIVES

#### 4.1 Primary Objectives:

- To compare the sensitivity, specificity, positive and negative predictive values of the ELISpotbased IGRA (T-SPOT.TB), the ELISA-based IGRA (QuantiFERON-TB Gold in-tube) and conventional diagnostic testing for the diagnosis of active pulmonary and extrapulmonary TB, in routine clinical practice;
- To develop an evidence-based optimal testing algorithm that defines the role of IGRAs in the diagnostic work-up of suspected active TB;
- To deliver the objectives above for a key subgroup: HIV co-infected patients (the highest risk subgroup of TB); and
- To quantify and compare the cost-effectiveness of a range of possible testing strategies against the present testing regime. Importantly, the benefit to individual patients and prevention of transmission to others (i.e. infections averted) will also be considered.

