### 6. PARTICIPANT ENTRY

#### 6.1. Pre-registration evaluations

Potential participants (patients presenting at participating NHS centres) will be referred to a TB Research Nurse by the attending clinician (see table below, detailing TB diagnostic criteria). A second participant screening process will then be carried out by the TB Research Nurse, to ensure that participants meet the set inclusion criteria. To be included in the study, participants will need to be aged 16 years-of-age or over and present with suspected active TB (pulmonary or extra pulmonary), at either an inpatients or outpatients department.

**Table 1.0** Pre-defined composite reference standard for active tuberculosis, validated in a prospective UK study in routine practice.

Diagnostic Category	Criteria
1: Culture-confirmed tuberculosis	Microbiological culture of Mycobacterium tuberculosis and suggestive clinical and radiologic findings
2: Highly probable tuberculosis	M. tuberculosis culture negative but clinical and radiologic features highly suggestive of tuberculosis and unlikely to be caused by other disease and supportive histology and/or cytology if available and a decision to treat has been made and appropriate response to therapy
3: Clinically indeterminate	A final diagnosis of tuberculosis was neither highly probable nor reliably excluded with no alternative diagnosis and the patient was not subsequently diagnosed with TB within 6 months
4: Active tuberculosis excluded	All microbiological samples smear and culture negative and a definite alternative diagnosis identified and the patient was not subsequently diagnosed with TB within 6 months

During the second participant screening process, the TB Research Nurse will also determine whether to exclude participants from the study. The exclusion criterion includes a participant being aged less than 16 years-of-age, any previous treatment for TB, or an inability to provide informed consent.

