#### 10.3 Data Analysis

Sensitivity, specificity, positive and negative predictive values and likelihood ratios for each test and combination of tests, will be calculated to determine diagnostic accuracy and clinical utility for the representative cohort as a whole and within the appropriate subgroup of HIV co-infected patients. Participants to be included with reference to standard results from categories 1 (culture-confirmed), 2 (highly probable), and 4 (active tuberculosis excluded) for the primary analyses. Categories are described in table 1.0. The proportion of participants in Category 3 (clinically indeterminate) will be reported, and their impact on estimates ascertained by including them in sensitivity analyses. Similarly, sensitivity analyses will be carried out to investigate the impact of including Category 2 participants, particularly regarding test sensitivity. Full disclosure of all results will be reported, including numbers of indeterminate ELISpot and ELISA results.

Comparisons between ELISA and ELISpot IGRA tests will be provided to exploit the paired nature of data, using repeated measures and marginal logistic regression models, utilising the reference standard as an outcome. In the subset of patients presenting with a TST as part of their clinical diagnostic work-up, the performance of this particular test will be compared with IGRA results. Variation in test performance with HIV status and other characteristics will be estimated by including covariates in the models.

The performance of combinations of two or more tests using logistic regression models constructed in the same form as Bayesian updating (post-test odds = pre-test odds x likelihood ratio) by including the log of the pre-test odds of prevalence (a constant term of known value) as an offset in the model, will be assessed. A linear predictor will then estimate log likelihood ratios, rather than log odds ratios. However, bootstrap methods will be required to obtain valid CIs (confidence intervals). Model parameterizations from Knottnerus to compute likelihood ratios for the additional diagnostic value of each test in a testing sequence, will be used. Non-parametric, bias-adjusted CIs for parameter estimates from 1,000 bootstrap samples will be computed.

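### Smear and culture are built into the reference standard, so in the primary analysis set their specificity and PPV under primary objective 1 are 100% by construction

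*Protocol*

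**What the plan says.** The first primary objective (section 4.1) places three things side by side on sensitivity, specificity, PPV and NPV: the ELISpot assay, and "QuantiFERON-TB Gold in-tube) and conventional diagnostic testing for the diagnosis of active pulmonary and extrapulmonary TB, in routine clinical practice". The objective does not list which tests make up the conventional arm. The nearest description is in section 3.2: "Current conventional methods of diagnosing active TB primarily rely upon the identification of bacilli through microscopy, nucleic acid amplification and culture". The same section adds clinical and radiological features, histology, and that "on occasion the use of the tuberculin skin test (TST) can also be used to determine infection status".

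The yardstick is given in section 3.1: "The study will be measured against a validated pre-defined composite reference standard for active tuberculosis". Table 1.0 in section 6.1 defines it:

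- Category 1 (TB) needs a positive M. tuberculosis culture "and suggestive clinical and radiologic findings".
- Category 2 (TB) is "culture negative but clinical and radiologic features highly suggestive of tuberculosis and unlikely to be caused by other disease", together with a decision to treat and a response to therapy.
- Category 3 is indeterminate, with no alternative diagnosis.
- Category 4 (TB excluded) needs "All microbiological samples smear and culture negative and a definite alternative diagnosis identified", and no TB diagnosis within 6 months.

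Section 10.3 takes "categories 1 (culture-confirmed), 2 (highly probable), and 4 (active tuberculosis excluded) for the primary analyses". Category 3 enters only in sensitivity analyses.

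**The concern.** A test cannot be given a fair false-positive rate against a non-diseased group that was selected to be negative on that test. Smear and culture are at the centre of what the protocol calls conventional diagnosis, and a negative result on both is a condition of entry to Category 4. The IGRAs are outside the standard, and their results are withheld from clinicians (section 9.2), so they can err in either direction. The only safeguard described (section 5.1) is against IGRA results influencing the diagnosis. Nothing in the protocol mentions that conventional tests are incorporated in the standard.

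At stake is the meaning of part of a primary objective, which is repeated for HIV co-infected patients. Followed as written, the plan would report a specificity and a PPV contrast between IGRAs and smear/culture in which one side was settled before any data were collected.

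**Working it through.** **The plan's own figure.** Section 10.2 gives 855 patients for sensitivities of 85% and 75%, 5% two-sided, 90% power and 40% prevalence, paired with independent errors.

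- Discordance: 0.85 × 0.25 + 0.75 × 0.15 = 0.325. Difference: 0.10.
- TB cases: (1.96 + 1.2816)² × 0.325 / 0.10² = 341.5, rounded up to 342.
- Patients: 342 / 0.40 = 855, as stated.

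For the HIV subgroup (85% and 65%, 80% power, 50% prevalence), the discordance is 0.85 × 0.35 + 0.65 × 0.15 = 0.395. TB cases are (1.96 + 0.8416)² × 0.395 / 0.20² = 77.5, rounded up to 78, and 78 / 0.50 = 156, as stated. Both concern one IGRA against the other, so neither depends on the point made here.

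**The 2×2 table in the primary set.** Diseased = Categories 1+2; non-diseased = Category 4.

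- Smear or culture positive in Category 4: FP = 0 by definition.
- Specificity = TN / (TN + 0) = 100%.
- PPV = TP / (TP + 0) = 100%, as long as there is at least one positive.
- Every Category 1 patient is culture positive and every Category 2 patient culture negative, so culture sensitivity = n(Category 1) / [n(Category 1) + n(Category 2)]. It varies with the data but only restates how cases were classified. Smear sensitivity has no such identity, since smear-positive cases can fall in either category.

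**With numbers.** Take 855 analysed patients at 40% prevalence: 342 TB and 513 non-TB. The documents do not give the share of TB cases that is smear or culture positive, so assume 40% to 90%.

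| Share of TB cases positive | Sensitivity | Specificity | PPV | NPV |
|---|---|---|---|---|
| 40% | 40% | 100% | 100% | 513 / (513 + 205.2) = 71.4% |
| 60% | 60% | 100% | 100% | 513 / (513 + 136.8) = 78.9% |
| 90% | 90% | 100% | 100% | 513 / (513 + 34.2) = 93.75% |

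Sensitivity and NPV move; specificity and PPV cannot.

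**Where false positives go.** A smear-positive patient with a definite non-TB diagnosis fails Category 4 (not all smears negative) and Category 3 (an alternative diagnosis exists). Without the features or treatment response of Categories 1 and 2, the patient has no category and leaves the analysis. These are the patients who would show a smear false positive.

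**Sensitivity analysis with Category 3 counted as non-TB.** Assume Category 3 is 5% to 20% of 855 patients, 0% to 10% of them are smear or culture positive, 40% of the remainder have TB, and 60% of those are test positive. At the far end:

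- Category 3 = 171; the rest = 684, of whom 273.6 have TB.
- Non-TB = 410.4 + 171 = 581.4; FP = 17.1; TP = 164.16.
- Specificity = 1 − 17.1/581.4 = 97.1%; PPV = 164.16/181.26 = 90.6%.

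Across the assumed range, specificity is 97.1% to 100% and PPV 90.6% to 100%. The forced value therefore belongs to the primary set.

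**The case against.** The best defence is that the affected measures are not where the study puts its weight. Section 10.3 says interpretation will centre on sensitivity, negative likelihood ratio and NPV, and for smear and culture the forced 100% leaves sensitivity and NPV free to vary. The only powered comparison is ELISpot against ELISA. The paired models in section 10.3 are for those two assays, and no test of IGRA specificity against smear or culture is laid down. Likelihood ratios for the additional value of each test in a sequence are already planned. Footnote c to Figure 2.0 describes exclusion of TB without a smear condition, so the missing category may be a slip of wording, and no count of such patients is given. All of this stands and lowers the severity. It does not remove the defect: specificity and PPV are named in the primary objective, and the non-TB group is fixed by Table 1.0.

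A reader might infer several stronger things that the documents do not support:

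- *Conventional testing as a whole scores 100% on all four measures.* The full work-up is never defined as an index test. The standard also uses treatment response and six-month follow-up, which are unknown at presentation, so a work-up diagnosis can differ from the final category.
- *Only the IGRAs can be wrong in both directions.* Skin testing and nucleic acid amplification are not named in Table 1.0. Section 3.2 itself describes false positives and poor sensitivity for the skin test. That a skin test swayed a Category 2 judgement is possible but nowhere stated.
- *Any IGRA specificity deficit is an artefact.* If IGRA specificity were 80% (an assumption), the gap would be 20 points, but the artefact is only 100% minus the true specificity of smear or culture. Section 3.2 regards those techniques as highly specific, and section 3.2 also expects IGRAs to be poorly specific for active TB. Most of such a gap would be real.
- *The cost-effectiveness results are biased.* The protocol does not state the model's inputs, so this is conjecture.

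**Conclusion.** The concern holds in a narrow form. In the primary analysis set (Categories 1, 2 and 4), smear and culture specificity and PPV are exactly 100% by definition, and culture sensitivity restates the split between Categories 1 and 2. This follows from Table 1.0 and section 10.3 alone and needs no numerical assumption. Two of the four measures in the IGRA-versus-smear/culture part of primary objective 1 are therefore uninformative, and the protocol does not acknowledge it. In addition, on a literal reading, smear-positive patients with a definite non-TB diagnosis are dropped; how many cannot be told from the documents.

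Radiology, histology and clinical features are also part of the standard. That is incorporation bias, but it does not fix their specificity at any value. The sample sizes of 855 and 156 and the ELISpot-versus-ELISA sensitivity comparison are unaffected. This is a specific and inexpensive correction that should be made, and it does not threaten the study's powered result.

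**What to change.** 1. In objective 1 and section 10.3, name the conventional index tests.
2. Drop the specificity and PPV contrasts between the IGRAs and smear or culture.
3. Report smear and culture sensitivity in Categories 1+2 descriptively, stating the incorporation bias.
4. Answer the IGRA-versus-conventional question as added value, using the sequential likelihood-ratio models already planned in section 10.3.
5. Reword Category 4 in Table 1.0 as negative for M. tuberculosis, so that non-TB patients with a positive smear or another organism stay in the non-TB group. This makes smear false positives possible again. It does not free culture specificity, which stays fixed, so step 2 is still needed.

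The cost is wording in objective 1, section 10.3 and Table 1.0, with no change in sample size. The downside is a narrower claim about how IGRAs compare with conventional testing.

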#### **10.2 Sample size calculation**

The primary clinical utility of IGRA results in assessment of suspected active TB is in their negative predictive value, which enables clinicians to reliably rule-out TB from the differential diagnosis. This in turn depends on the diagnostic sensitivity and the prevalence of TB in the tested population. A recent meta-analysis computed diagnostic sensitivity of T-SPOT.TB and QFT-in tube in active TB as 90% and 70% respectively. However, these estimates are based on pooling together several small datasets. The two largest studies to-date (n=194 TB cases diagnosed from n=389 TB suspects; n=216 TB cases diagnosed from n=413 TB suspects) gave more robust estimates of 85.1% (95% CI 79.2, 89.9) and 85.2% (95% CI 76.1, 91.9) for T.SPOT.TB for the respective studies and 78.1% (95% CI 70.7, 84.3) for QuantiFERON-Gold in-tube.

This study has been powered to detect a conservatively estimated 10% difference in diagnostic sensitivity between the tests, assuming a sensitivity of 85% for T-SPOT.TB and 75% for QFT-in tube and skin testing. To detect this difference at the 5% significance level (2-tailed) with 90% power, 855 patients are required (each receiving both tests), assuming a 40% prevalence of active TB in the study population. The number of patients recruited will be 1,012 to allow for missing data, indeterminate results, withdrawal of consent and possible logistical errors. These calculations have been made using methods which account for the paired nature of the data (based on McNemar's test) assuming independence of test errors.

In the HIV-infected subgroup, published evidence indicates that diagnostic sensitivity of QFT-in tube is reduced while that of T-SPOT.TB is unaffected. It is estimated that diagnostic sensitivities will be of 85% and 65% for T.SPOT.TB and QFT-in tube respectively, with this study powered to detect such a difference, at the 5% significance level, assuming a 50% prevalence of active TB in the HIV-infected subgroup; 156 patients are required to give 80% power and we expect to recruit 200 patients.

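### The protocol describes no optimism correction for the accuracy of the 'optimal' testing algorithm; the likely overstatement is modest and largely confined to the HIV subgroup

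*Protocol*

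**What the plan says.** Protocol section 4.1 lists among the primary objectives: "To develop an evidence-based optimal testing algorithm that defines the role of IGRAs in the diagnostic work-up of suspected active TB". The next item extends this to one subgroup: "To deliver the objectives above for a key subgroup: HIV co-infected patients".

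Section 10.3 gives the method. It will assess "The performance of combinations of two or more tests using logistic regression models constructed in the same form as Bayesian updating", with the log pre-test odds as an offset and likelihood ratios for the added value of each test in a sequence. The bootstrap is introduced because it is needed for valid confidence intervals, and its use is then fixed: "Non-parametric, bias-adjusted CIs for parameter estimates from 1,000 bootstrap samples will be computed".

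The possible components are the two commercial IGRAs, the enhanced ELISpot run on all participants (section 7.3), the skin test in those who have one (section 10.3) and conventional testing. Section 10.3 also provides for manufacturers' cut-offs on the commercial assays, ROC analysis of response size, and a study of the ratio of spot-forming cells to CD4 count in HIV-infected patients.

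One cohort is described: "The number of patients recruited will be 1,012 to allow for missing data, indeterminate results, withdrawal of consent and possible logistical errors". Of these, 200 are expected to be HIV-infected. The protocol describes no split sample, cross-validation or validation cohort, and gives no criterion for calling an algorithm optimal.

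**The concern.** An optimal algorithm has to be chosen from several candidates. If it is chosen because it performs best in these patients and its accuracy is then estimated in the same patients, part of its apparent lead is chance, and the estimate is too high on average. A bootstrap of a fixed model's parameters resamples patients but leaves the choice untouched, so its bias adjustment does not see the selection. Only resampling that repeats the choice does.

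The bias falls on what matters most here. Section 10.3 says interpretation will centre on sensitivity, negative likelihood ratio and NPV, because the purpose is to exclude TB. An NPV that is 1 point too high hides one missed case per 100 patients with a negative result. The HIV subgroup is the smaller sample, and section 3.3 promises recommendations for it.

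**Working it through.** **1. The protocol's own figures.** Section 10.2 uses a paired McNemar calculation with independent errors. Cases needed = (z_alpha/2 + z_power)² × (p10 + p01) / (p1 − p2)², rounded up and divided by prevalence.

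- Whole cohort, "assuming a sensitivity of 85% for T-SPOT.TB and 75% for QFT-in tube and skin testing": p10 = 0.85 × 0.25 = 0.2125 and p01 = 0.15 × 0.75 = 0.1125. At 90% power: (1.960 + 1.282)² × 0.325 / 0.10² = 341.5, so 342 cases, and 342 / 0.40 = 855. This matches "To detect this difference at the 5% significance level (2-tailed) with 90% power, 855 patients are required".
- HIV subgroup, 85% against 65%: p10 = 0.85 × 0.35 = 0.2975 and p01 = 0.15 × 0.65 = 0.0975. At 80% power: (1.960 + 0.842)² × 0.395 / 0.20² = 77.5, so 78 cases, and 78 / 0.50 = 156. This matches.

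Both figures reproduce. They size one comparison of two single tests. They do not cover choosing an algorithm.

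**2. Sample available for choosing.** Whole cohort: 1,012 × 0.40 ≈ 405 cases and 607 non-cases. HIV: 200 × 0.50 = 100 cases and 100 non-cases, before Category 3 patients are left out of the primary analysis.

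**3. Size of the optimism, by simulation.** Optimism is the apparent minus the true performance of the selected rule, averaged over simulated cohorts.

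- From section 10.2: HIV sensitivities of 85% and 65%, and the subgroup size of 200.
- Assumed: a third test with 89% sensitivity, a fourth with 65%, specificities of 75–80%, and latent correlation between tests of 0.3–0.7.
- Assumed rule set: each test alone, any-positive and all-positive for every combination. Two tests give 3 + 1 = 4 rules, three give 7 + 4 = 11, and four give 15 + 11 = 26.
- Assumed choice: the highest sensitivity plus specificity or, for NPV, the highest NPV.

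| Setting | Overstatement |
|---|---|
| HIV 100/100, three or four tests: sensitivity + specificity | about 2–3 points (separate runs gave 1.8–2.3 and 2.2–2.5) |
| HIV 100/100, three or four tests: NPV | about 0.7–1.8 points |
| HIV 100/100, two commercial IGRAs only: sensitivity + specificity | about 0–1 point |
| Whole cohort: sensitivity + specificity | under 1 point |

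**4. Dependence on assumptions.** Closer candidates and fewer patients raise the figure. With HIV sensitivities of 75–89% instead of the protocol's 85% and 65%, and only 78/78 patients, it is 3.4–4.8 points. With 3 to 20 exactly equal strategies (true values 85%/70%, correlation 0–0.8), it is 3.4–10.7 points in HIV at 100/100 and 1.4–4.7 points in the whole cohort. Those last ranges are an upper bound: exact equality conflicts with the 20-point HIV gap and the 10-point overall gap on which section 10.2 is built.

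**5. Scale.** The 95% interval half-width for a sensitivity of 85% in 100 cases is 1.96 × √(0.85 × 0.15 / 100) = 0.070, or 7 points. The optimism is smaller than the sampling error. Unlike sampling error it has a fixed direction, and the planned intervals do not allow for it.

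**The case against.** The strongest reply is that much of this is inferred from silence. The protocol never says that the chosen algorithm's accuracy will be reported uncorrected, and a separate analysis plan, not available here, may contain internal validation. That stands: a reader might infer uncorrected reporting, but the document supports only that no correction is described. What remains is that section 10.3 goes into analysis-plan detail, specifies 1,000 resamples, and gives them a narrower job than the primary objective needs.

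Second, no search over any-positive and all-positive rules is planned. Section 10.3 plans likelihood ratios for successive tests and promises full disclosure of all results, so competitors will be visible beside the winner. This also stands. It makes the figures conditional, but disclosure does not correct the winner's own estimate.

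Third, a reader might infer that data-driven ROC cut-offs inflate the commercial assays' accuracy. The protocol does not support that: manufacturers' thresholds define positive and negative results, and ROC analysis describes what response size contributes. The concern would arise only if a threshold were chosen from the data, for example for the CD4 ratio, for which the protocol gives no cut-off.

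Fourth, a reader might infer that the whole economic analysis rests on the winner's inflated figures. Sections 3.1 and 3.3 cost each testing strategy, so only the chosen algorithm's inputs are exposed to selection bias.

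**Conclusion.** The point holds in a limited form. The protocol makes an optimal algorithm a primary objective, overall and in HIV co-infected patients, describes a single cohort, and assigns its bootstrap only to intervals for parameter estimates. As described, that bootstrap would not remove the bias from choosing the best-looking combination.

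Under the stated assumptions the effect is modest and lies mainly in the HIV subgroup when three or four tests compete. It is small with the two commercial assays alone and in the whole cohort. These sizes rest on an assumed candidate set, selection rule, specificities and correlation, because the protocol gives none of them. The broader reading, that the study's accuracy results as a whole are inflated, is not supported: estimates for single tests at manufacturers' cut-offs and the powered comparison of sensitivities involve no such selection.

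**What to change.** Amend section 10.3 as follows:

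1. List the candidate testing strategies and state the criterion by which one will be called optimal, for the whole cohort and for the HIV subgroup.
2. In each of the 1,000 bootstrap samples already planned, repeat the whole selection, including any data-chosen threshold, such as one for the spot-forming-cell to CD4 ratio if one is used. Record the chosen rule's accuracy in the bootstrap sample minus its accuracy in the original sample. Subtract the mean difference from the apparent accuracy.
3. Report optimism-corrected sensitivity, specificity, NPV and negative likelihood ratio for the chosen algorithm, above all in the HIV subgroup, and use the corrected values for that algorithm in the economic model.

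No further patients, samples or data are needed. The cost is analysis and computing time, and slightly less favourable reported figures for the chosen algorithm.
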